8.3.2 Periodic reporting of adverse events by sponsor

A summary of all IND safety reports will be included in the progress report submitted annually to the competent authorities within 60 days of the annual anniversary of the date, the IND went into effect. The same report will also be submitted to the IRB(s) to ensure a continuing review of the project.

8.4 IMMEDIATE REPORTING BY INVESTIGATOR TO SPONSOR

8.4.1 Reporting of SAEs

SAEs during the clinical observation period as well as relevant SAEs or SARs during the follow-up phase must be documented on a ‘Serious Adverse Event/Expedited Report for Combination Products from a Clinical Trial form’ in accordance with instructions for completing the ‘Serious Adverse Event/Expedited Report for Combination Products from a Clinical Trial form’. This form and the instructions will be provided in the investigator file and must be completed and supplied immediately to the sponsor (21CFR§ 312.32, 21CFR§ 312.64).

Any SAE that occurs during the clinical observation period of the study, whether or not related to the IMP or the medical device, and any relevant SAE or SAR during the follow-up phase must be reported by the investigator within 24 h by fax, or by e-mail, to the following persons:

Email: [REDACTED]

Fax: [REDACTED]

The initial report must be as complete as possible, including details of the current illness and (serious) AE, and an assessment of the causal relationship between the event and the IMP(s) or medical device or study procedures.

Information not available at the time of the initial report (e.g. an end date for the AE or laboratory values received after the report) must be documented on a ‘Serious Adverse Event/Expedited Report for Combination Products from a Clinical Trial form’, with the box “Follow-up” checked under “Report type”.

The instructions for completing the ‘Serious Adverse Event/Expedited Report for Combination Products from a Clinical Trial form’ give more detailed guidance on the reporting of SAEs, AEs that comply with alert terms, and AEs initially reported as non-serious that become serious. In the latter situation, when a non-serious event becomes serious, details must be forwarded immediately to the sponsor on a “Serious Adverse Event/Expedited Report for Combination Products from a Clinical Trial” form.

Pregnancies occurring during a subject's participation in the study, although not typically considered SAEs, must be notified to the sponsor within the same timelines as an SAE (within 24 h after becoming aware of the pregnancy) on a pregnancy notification form. If possible, the clinical visits as well as the FU visits should be completed, but no further PDT must be applied. Further treatment will be addressed on a case-by-case basis with the treating physician and the investigator.

Any pregnancy should be followed up until completion. If relevant, the development of the newborn will be monitored for an appropriate time post-delivery.

The drug safety department of the sponsor or designee has to be notified by fax or e-mail.

The sponsor will ensure that all legal reporting requirements to the competent authorities and the IRB(s) are met.

Note:

For regulatory reporting purposes, events which are assessed by the sponsor as “unrelated” or “unlikely related” to the study medication will be considered as having no reasonable causal relation and will not be reported on an expedited basis.

Events assessed by the sponsor as “possibly, probably or definitely related” will be considered as having a plausible causal relation to the study medication and will be reported if they are also considered unexpected and serious.

8.4.2. Reporting of USADEs to the IRB

Events which can be clearly assigned to the medical device and which are assessed by the investigator as “possibly, probably or definitely related” to the medical device and which are both serious and unanticipated will be considered as unanticipated adverse device effect (USADE). A report of any unanticipated adverse device effect occurring during an investigation shall be submitted to the reviewing IRB within 10 working days after the investigator first learns of the effect (21 CFR §812.150).

In case a serious and unexpected event which cannot clearly assigned to the medical device BF-RhodoLED®, it should be treated as an SAE (see [Section 8.4.1](#)).

Note: Reporting of USADEs to the sponsor is equal to SAE reporting described in section 8.4.1.

8.5 UNBLINDING DUE TO REGULATORY REPORTING OR INVESTIGATOR

If the unblinding (during the clinical observation period) is performed by the investigator due to a medical requirement, the subject will discontinue trial participation.

If applicable and required, treatment codes will be unblinded prior to submission to authorities and concerned ethics committees, by the sponsor’s safety group, which is an independent entity within the sponsor.

Reporting obligations to the local IRBs of the investigator will be fulfilled by the investigator, unless otherwise specified.

8.6 CONTINUOUS RISK ASSESSMENT

The sponsor’s safety department will apply appropriate monitoring measures to continuously survey the benefit risk ratio of the investigational medicinal product, the medical device and study procedures.

9 WITHDRAWALS

9.1 WITHDRAWAL OF SUBJECTS

Subjects must be withdrawn from the study (i.e. from any further study procedure) for the following reasons:

- At their own request (withdrawal of informed consent).
- If, in the investigator's opinion, continuation in the study would be detrimental to the subject's well-being.

Subjects must be withdrawn from the IMP under the following circumstances:

- Pregnancy (applies only during the clinical observation period of the study).
- If new lesions that develop in close proximity to a treated lesion after the 1st PDT require immediate treatment in the opinion of the investigator (during clinical observation period of the study).
- In case of a SUSAR or USADE.

In all cases, the reason for and date of withdrawal must be documented. Subjects are not obliged to specify a reason for their withdrawal. If they refuse to do so, the withdrawal should be documented as "withdrawal of consent". The subject must be followed up to establish whether the reason was an AE, and, if so, this must be documented in accordance with the procedures in [Section 8](#).

As far as possible, all examinations scheduled for the final study day should be performed on all subjects who receive the IMP but who do not complete the study according to protocol.

The investigator must make every effort to contact subjects lost to FU. Attempts to contact such subjects must be documented in the subject's records (e.g. at least 3 times and dates of attempted telephone contact, receipt for sending a registered letter).

For subjects that may not be randomized due to screening failures or who decide to terminate the study prior to randomization, at least the following parameters must be documented in the eCRF: date of informed consent, demographics and date and reason for withdrawal.

9.2 REPLACEMENT OF SUBJECTS

Randomized subjects will not be replaced after they have discontinued the study.

9.3 WITHDRAWAL OF SAMPLES

Not applicable.

10 EMERGENCY PROCEDURES

10.1 EMERGENCY SPONSOR CONTACT

In emergency situations, the investigator should contact the sponsor by telephone at the number given on the title page of the protocol or in [Section 8.4](#), if that is regarded as necessary.

10.2 EMERGENCY IDENTIFICATION OF INVESTIGATIONAL PRODUCTS

There is no apparent reason to break the randomization code in the event of an adverse drug reaction. The subjects receive all treatments on only small treatment areas. In the case of an adverse reaction triggered by the respective treatment, no further treatment is scheduled. There is no substance-specific treatment for adverse reactions. Therefore, special emergency identification procedures are not applicable to this trial.

In case the investigator still needs to unblind for a specific randomization number, this can be done via an interactive web response system (IWRS). The qualified person for pharmacovigilance (QPPV) as well as the responsible project manager at Biofrontera Bioscience GmbH will immediately be informed about the code braking by the system. In case a subject needs to be unblinded, the affected subject is not allowed to receive retreatment, e.g. at Visit 3 or in case that the subject presents non-responding lesions at Visit 5 or Visit 6 (partial or non-responder after the 1st PDT cycle). The subject must be withdrawn from the study.

10.3 EMERGENCY TREATMENT

During and after a subject's participation in the trial, the investigator or institution should ensure that adequate medical care is provided to a subject for any AEs, including CS laboratory values, related to the trial. The investigator or institution should inform a subject when medical care is needed for intercurrent illness(es) of which the investigator becomes aware.

11 STATISTICAL PROCEDURES

The statistical planning of the study, and the statistical analyses will be conducted following the principles as specified in the International Conference on Harmonization of Technical Requirements for Registration of Pharmaceuticals for Human Use (ICH) Topic E9 (ICH, 1998), and will be carried out by a qualified statistician in accordance with the ICH guidelines and adequate biostatistical SOPs. The statistical analyses will be performed separately for the clinical observation part of the study, which includes the clinical observation period (1st and 2nd PDT cycle), and for the FU part of the study. The statistical analysis of the clinical observation period of the study (up to Visit 8) will be performed after database lock and subsequent unblinding of all data to the statistician, data manager, and sponsor. The statistical analysis of the FU part of the study will be performed after database locks for the 12, 24, 36 and 60 months data, respectively.

Technical details of the statistical analyses will be specified in separate statistical analysis plans (SAPs). The SAP for the clinical observation period of the study will be generated in parallel to the clinical study protocol. The SAP for the FU part of the study will be finalized prior to the database lock for the 12-month data time point.

A confirmatory hypothesis test will be performed for the primary and the key secondary efficacy endpoint only. A Cochran-Mantel-Haenszel Test with stratification factors lesion baseline characteristics (lesion count 1 vs ≥ 2 lesion(s)) and center will be used to test the primary hypothesis on a significance level of 0.1% ($\alpha=0.001$; one-sided) on the full analysis set (FAS). The primary analysis will be repeated for the PPS as sensitivity analysis. Additional key secondary efficacy variables will be tested confirmatory using a hierarchical testing procedure using the FAS, whereas further secondary efficacy variables will be tested descriptively and in an exploratory manner.

Confirmatory hypothesis testing of key secondary variables measured during the double-blind clinical observation period will be done only after the test of the primary efficacy variable is passed, and will be done strictly in the given order to ensure the FWER. Hypothesis testing in the pre-defined order will stop once the first non-significant test result is obtained.

For further secondary endpoints, two-sided statistical testing procedures will be conducted using a significance level of 5% ($\alpha=0.05$). Additionally and where appropriate, two sided local 95% CIs of differences between BF-200 ALA and vehicle will be presented. As the secondary endpoint analysis, including the calculation of CIs are not confirmatory, an adjustment for multiplicity is not considered necessary.

Unless otherwise stated, continuous data will be summarized by means of descriptive statistics, i.e. number of subjects, mean, standard deviation (SD), median, quartiles and range (minimum and maximum). Categorical variables will be summarized by absolute and relative frequencies (percentages) of subjects by category.

Statistical analyses will be conducted using SAS version 9.3 or higher (SAS Institute, 2010).

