5.3 RANDOMIZATION AND TREATMENT ASSIGNMENT

The IMP will be administered exclusively to subjects matching the eligibility criteria and for whom the written informed consent and HIPAA form is available (see [Section 12.3](#)).

Each subject for whom informed consent and HIPAA is obtained will be assigned a subject number in the chronological order of enrollment (within each center). This subject number will be documented and will be used to identify the subject until he/she is either found to be eligible for the study and is then assigned with a randomization number or is identified as a screening failure (i.e. the subject is not eligible for the study). The randomization will be stratified according to the number of eligible lesions (1 vs ≥ 2). Additionally the randomization procedure will ensure a stratification by center. The randomization number will be assigned accordingly and will be provided by the eCRF platform upon entering the total number of eligible lesions to be included in the study.

Subjects will be randomized at a 4:1 allocation ratio of active treatment (BF-200 ALA) to control (vehicle). Randomization numbers will be blocked. The block size will not be revealed but a detailed description of the randomization including block size will be provided in a separate randomization plan (not provided to sites). A minimum of 10 to a maximum of 30 subjects should be randomized per study site but no site should randomize more than 20 subjects unless prior approval of the sponsor is obtained.

The randomization schedule and the allocation to treatment groups will not be known by the sponsor until completion of the clinical observation period of the study, except in case of an emergency. The randomization schedule and the allocation to treatment groups will remain unknown to the investigator until completion of follow-up. In case of emergency the investigator can request unblinding of a specific randomization number via an interactive web response system (IWRs). The qualified person for pharmacovigilance (QPPV) as well as the responsible project manager at Biofrontera Bioscience GmbH will receive immediate notice from the system about the code breaking. There is no apparent reason to break the randomization code in the event of an adverse drug reaction. This is because the subjects receive all treatments on only small treatment fields two or four times within 3 months and there is no substance-specific treatment for adverse reactions.

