#### 1 General

This Statistical Analysis Plan (SAP) was defined by the CRO acting on behalf of sponsor and the responsible Statistician without knowledge of the randomization code. It is based upon the Study Protocol (version 3.0 of 17 July 2018) and contains a detailed description of the statistical methods described therein.

The statistical analyses will be performed separately for the clinical observation phase and the follow-up phase. This SAP describes prospectively the main analyses for the clinical observation phase, which will be performed after database lock and subsequent unblinding of all data after the end of the clinical observation period. The SAP version 1.0 was finalized in parallel to the study protocol version 2.0, before the first study subject received study medication. Additional data from the follow-up period (12, 24, 36 as well as 60 months after completion of the 1st PDT cycle (Visit 5)) will be analyzed and reported separately from the report of the clinical observation phase of the study. All details of the statistical analyses and methods for the follow-up period will be specified in a separate SAP.

This is a phase III, multicenter, randomized, vehicle controlled, double blind, parallel group study comparing BF-200 ALA with vehicle (4:1 ratio). The study is divided into 2 parts, part 1 is the clinical observation part, consisting of a screening period and a treatment period, part 2 covers the FU.

To guarantee the blind status of the investigator assessing the efficacy after each PDT cycle, a second investigator or delegated person will perform drug application and light treatment. The second investigator or delegated person will furthermore conduct all safety evaluations at visits where PDT is applied and during the phone call 1 week after each PDT cycle, respectively. Both investigators (and delegated person(s)) are not entitled to exchange information about the study outcome and side effects.

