## 4 Statistical Evaluation

Missing values of the primary endpoint will be regarded as non-responders. Missing values of clinical lesion assessments only will be imputed using a last observation carried forward (LOCF) approach. If no preceding assessment is available, the lesion will be regarded as non-responding. Further details of handling of missing data are described in section 4.6.

Unless otherwise stated, continuous data will be summarized by means of descriptive statistics, i.e. mean value, standard deviation (SD), first quartile, median, third quartile, range (minimum and maximum), and number of non-missing values. Categorical variables will be summarized by absolute and relative frequencies (percentages on non-missing values) of subjects by category.

Only data belonging to the clinical observation phase will be used for the analysis described in this SAP. For this, data of follow-up visits will be excluded from SDTM data sets used for analysis of clinical observation phase. For visit-scheduled datasets (incl. medical history), all records prior to or at Visit 8 (12 weeks post-PDT-3) - end of clinical study phase - will be included. Subjects with premature termination after Visit 8 will be removed from dataset "Study Termination" (i.e. they will not be identified as drop-outs). Furthermore, adverse events (AEs) and concomitant medications (CMs) starting after date of last visit/assessment of clinical phase (maximum date of all visit/assessment dates within non-log forms prior to or at Visit 8) on subject level will be excluded. If the month and/or day of the start date of AE or CM is not available, a worst-case-approach will be included when that assumed date is prior or at the maximum date of all visits and assessments prior to or at Visit 8. If the complete start date is not known, a worst-case-approach will be applied, and a date of 2000-01-01 will be assumed, to ensure that it will be prior to the maximum date of all visits and assessments prior to or at Visit 8.

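### The follow-up SAP may be finalized after the clinical-phase unblinding, while the rule for losses and the conflicting recurrence wording are still open

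*Protocol*

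**What the plan says.** **Order of events.** Protocol 11 says the analysis of the clinical observation period "will be performed after database lock and subsequent unblinding of all data to the statistician, data manager, and sponsor". The follow-up analyses "will be performed after database locks for the 12, 24, 36 and 60 months data, respectively". One follow-up SAP serves all four, and its deadline is stated in 11 and again in 11.3: "The SAP for the FU part of the study will be finalized prior to the database lock for the 12-month data time point".

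**Blinding.** Under Protocol 5.3 the allocation "will not be known by the sponsor until completion of the clinical observation period of the study, except in case of an emergency". For the investigator it "will remain unknown to the investigator until completion of follow-up".

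**Where follow-up methods sit.** SAP 1 states: "All details of the statistical analyses and methods for the follow-up period will be specified in a separate SAP". SAP 4 provides that "data of follow-up visits will be excluded from SDTM data sets used for analysis of clinical observation phase", and that subjects who terminate after Visit 8 are removed from the termination dataset. It therefore expects follow-up records to be present when the clinical phase is analysed.

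**What the protocol already fixes.** Section 11.1.3 lists the recurrence variables with their denominators and makes them descriptive and exploratory. Sections 2.2 and 7.3.1 give general recurrence definitions. Section 11.2 names the follow-up analysis sets.

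**The concern.** The deadline is tied to an event that comes after unblinding. Nothing in either document requires the follow-up SAP before the codes are opened. By contrast, SAP 1 records that the clinical-phase SAP was prepared without access to the randomization code, and that its version 1.0 was final before the first subject was dosed.

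The choices exposed are those the protocol leaves unsettled:

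- **Losses and missed follow-up visits.** Protocol 11.4 and SAP 4.6 deal with the 5- and 12-week lesion assessments and with safety data. Neither has a rule for follow-up visits.
- **Estimators** for the recurrence rates.
- **Conflicting recurrence wording.** Someone has to choose between the versions, possibly knowing the arms.

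Protocol 7.2.3 gives long-term recurrence as the reason for the 5-year follow-up. At stake is the credibility of those durability figures.

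**Working it through.** **Inputs.** First subject in September 2018, last subject in May 2019, last subject out of the clinical phase November 2019, last follow-up visit August 2024 (Synopsis and 3.2). Visit 5 is 12 weeks after PDT-1. Visit 8 is 12 weeks after PDT-3, which starts at Visit 5 (Table 1). Follow-up visits are counted from Visit 5 at 12 ± 1, 24 ± 2, 36 ± 2 and 60 ± 2 months (7.2.3). The lag from last visit to lock is about 2 months, stated in 3.2 for the final lock only. Using it for other locks is an assumption, so a range is shown.

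**1. Reproduce the plan's dates.** Count months from September 2018; 12 weeks = 2.76 months; last subject in = month 8.

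- Last Visit 5: 8 + 2.76 = 10.8 (about August 2019).
- Last Visit 8: 8 + 2 × 2.76 = 13.5 (October/November 2019; plan: November 2019).
- Last 60-month visit: 10.8 + 60 = 70.8 (about August 2024; plan: August 2024).

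Both stated dates reproduce.

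**2. Length of the unblinded window.**

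Window = (last Visit 5 + 12 + lag to 12-month lock) − (last Visit 5 + 2.76 + lag to clinical lock) = 9.24 + lag to 12-month lock − lag to clinical lock.

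The accrual dates cancel. The last column assumes uniform accrual over the 8 months, with the first 12-month visit at month 2.76 + 12 = 14.8. Share = (13.5 + lag − 14.8) / 8, floored at 0.

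| Lag to clinical lock (months) | Window, 12-month lock lag 0 | Window, lag 2 | 12-month visits due at unblinding |
|---|---|---|---|
| 0 | 9.2 | 11.2 | 0% |
| 1 | 8.2 | 10.2 | 0% |
| 2 | 7.2 | 9.2 | 9% |
| 3 | 6.2 | 8.2 | 22% |
| 4 | 5.2 | 7.2 | 34% |
| 6 | 3.2 | 5.2 | 59% |

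The range is about 3 to 11 months, and about 9 with 2-month lags. For a single subject, the 12-month visit follows Visit 8 by 8 to 10.5 months (11 to 13 months minus 11 to 13 weeks), so the order does not depend on the calendar.

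**3. Which follow-up data could be seen.** With a 2-month lag the 12-month lock falls at month 10.8 + 12 + 2 = 24.8. The first 24-month visit is due at 2.76 + 24 = 26.8, or 24.8 at the early edge of its window. On planned dates, essentially only 12-month data precede the deadline.

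**4. Size of the loss rule.** From the sponsor's earlier trial, BF-200 ALA, sBCC lesions, FAS:

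| | Recurrence (Protocol 1.1) | Losses counted as recurrent (Protocol 11.6) | Ratio |
|---|---|---|---|
| 1 year | 5.8% | 8.8% | 8.8 / 5.8 = 1.5 |
| 2 years | 7.7% | 16% | 16 / 7.7 = 2.1 |

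This shows how far the reported rate in one arm moves. The effect on a between-arm comparison would depend on how losses differ by arm, which the documents do not give.

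**5. The recurrence wording side by side.**

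- *How recurrence is established.* Section 7.3.1 relies on clinical assessment. Section 11.1.3 refers the Main Target Lesion back to the clinical-plus-histological composite, although that lesion has been excised.
- *Who is in the subject-level rate.* Section 2.2 requires the Main Target Lesion to have been cleared as in the primary endpoint and the Additional Target Lesions to be clinically clear. Section 11.1.3 defines the denominator by Additional Target Lesions only. A subject with a single lesion qualifies under the first if cleared, but has no clear place under the second.

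**The case against.** The case against has real weight.

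- **Most of the framework is already fixed.** A reader might infer that every follow-up rule, including definitions and denominators, could be written unblinded. The documents do not support that: 2.2, 7.3.1, 11.1.3 and 11.2 set them out. Only the items under the concern remain open.
- **Five-year results are not exposed.** A reader might infer that 24- to 60-month recurrences could be seen before the rules are set. On planned dates they could not (step 3). The limit does depend on recruitment keeping to plan. The SAP's COVID-19 section and a printed date of 29Jul2024 suggest that the calendar slipped, but the documents do not show how the locks moved.
- **A deadline is a latest date.** The follow-up SAP is not among the documents, so nothing shows that it was in fact written unblinded. SAP 4 speaks of follow-up visit data; it does not show that recurrences were on file on any planned date.
- **Consequences are limited.** Follow-up is exploratory and reported separately. The investigators who assess recurrence stay blinded throughout. Outcome assessment is therefore protected and only analysis choices are exposed.
- **Pooled data are already informative.** With 4:1 allocation, 149 of 186 subjects (80%) are on active treatment, so blinded pooled recurrences largely reflect that arm. This stands in part, but a deadline at the clinical lock also precedes most follow-up visits: 9% are due by then with a 2-month lag.

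None of these points closes the gap between unblinding and the deadline. They limit its severity.

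**Conclusion.** The point holds in limited form. As written, the follow-up SAP can be completed about 3 to 11 months after the statistician, data manager and sponsor are unblinded, or about 9 months with 2-month lags to both locks. These figures assume a lag of 0 to 6 months to the clinical lock and 0 or 2 months to the 12-month lock. On planned dates the exposure is essentially to 12-month data.

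The open choices are the loss and missed-visit rule, the estimators and the reconciliation of the recurrence wording. The first can double a reported 2-year rate on the sponsor's own earlier figures, taking the 1.1 figures as those without losses counted as recurrent. Confirmatory type I error, sample size and power are untouched. Severity is modest, but the change is worth making because it costs so little.

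**What to change.** In Protocol 11 and 11.3, replace the deadline with a requirement that the follow-up SAP be finalized and signed before database lock and unblinding of the clinical observation period. Mirror this in SAP 1. If the full document cannot be ready, fix at least two items by then: one recurrence definition that reconciles 2.2, 7.3.1 and 11.1.3, and the rule for losses and missed follow-up visits. Label any later change as made after unblinding.

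On planned dates the new deadline falls between about November 2019 and January 2020, close to the first 12-month visits (November/December 2019), so few or no follow-up results would exist. The unblinded window falls to zero. The cost is drafting the follow-up SAP some months earlier; it needs no additional subjects, visits or data.
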